1.2 Study objectives and endpoints

The study objectives and endpoints for the primary CSR can be found in [Table 1.2-1](#).

Table 1.2-1 Objectives and related endpoints

Part A	
Primary Objective	Endpoint for primary objective

To demonstrate superiority of ensovibep, compared to placebo, in reducing time-weighted change from baseline in \log_{10} SARS-CoV-2 viral load through Day 8	
Time-weighted change from baseline (measured at Day 3, Day 5, and Day 8) in \log_{10} SARS-CoV-2 viral load in nasopharyngeal swabs through Day 8
Secondary Objectives	Endpoints for secondary objectives

- To assess the effect of ensovibep, compared to placebo, in reducing the occurrence of hospitalizations (≥ 24 hours of acute care) and/or emergency room visits related to COVID-19 or death from any cause up to Day 29
- To assess the effect of ensovibep, compared to placebo, in reducing COVID-19 symptoms up to Day 29
- To evaluate safety and tolerability of ensovibep
- To characterize the pharmacokinetics (PK) of ensovibep
- Proportion of patients experiencing hospitalizations (≥ 24 hours of acute care) and/or emergency room visits related to COVID-19 or death from any cause up to Day 29
- Time to sustained clinical recovery, defined as (a) all symptoms from the modified FDA COVID-19 symptom list scored as moderate or severe at baseline are subsequently scored as mild or absent, AND (b) all symptoms from the modified FDA COVID-19 symptom list scored as mild or absent at baseline are subsequently scored as absent, with no subsequent worsening up to Day 29
- Proportion of patients up to end of study with:
 - Treatment Emergent Adverse events (TEAEs)
 - Serious adverse events (SAEs), including death from any cause
 - AEs of Special Interest (AESIs),
- Vital signs
- Clinical laboratory measurements
- Free and total ensovibep concentration in serum and calculated PK parameters

Exploratory Objectives

Endpoints for exploratory objectives

Part B

Primary Objective	Endpoint for primary objective

To demonstrate superiority of ensovibep, compared to placebo, in reducing the occurrence of hospitalizations (\geq 24 hours of acute care) and/or emergency room visits related to COVID-19 or death from any cause up to Day 29	
Proportion of patients experiencing hospitalizations (\geq 24 hours of acute care) and/or emergency room visits related to COVID-19 or death from any cause up to Day 29
Secondary Objectives	Endpoints for secondary objectives

To assess the effect of ensovibep, compared to placebo, in reducing SARS-CoV-2 viral load through Day 8To assess the effect of ensovibep, compared to placebo, in reducing COVID-19 symptoms up to Day 29To evaluate the immunogenicity of ensovibep during the studyTo evaluate safety and tolerability of ensovibep	
Time-weighted change from baseline (measured at Day 3, Day 5, and Day 8) in \log_{10} SARS-CoV-2 viral load in nasopharyngeal swabs through Day 8Time to sustained clinical recovery, defined as (a) all symptoms from the modified FDA COVID-19 symptom list scored as moderate or severe at baseline are subsequently scored as mild or absent, AND (b) all symptoms from the modified FDA COVID-19 symptom list scored as mild or absent at baseline are subsequently scored as absent, with no subsequent worsening up to Day 29Proportion of patients exhibiting treatment-emergent ADAs (TE-ADA) over timeProportion of patients up to end of study with:
Treatment Emergent Adverse events (TEAEs)Serious adverse events (SAEs), including deaths from any causeAEs of Special Interest (AESIs)Vital signsClinical laboratory measurements
Exploratory Objectives	Endpoints for exploratory objectives

[REDACTED]

[REDACTED]

- To evaluate the effect of ensovibep, compared to placebo, on general health status
- Absolute MCS and PCS scores from Short Form Health Survey (SF-36) questionnaire over time

[REDACTED]

[REDACTED]

2 Statistical methods

2.1 Data analysis general information

All CSR analyses of Part A and B will be performed by DATAMAP GmbH. The most recent version of SAS and R available in the statistical programming environment of DATAMAP will be used for the analysis.

The following general data conventions will apply:

- For the Part A primary analysis, performed when all patients completed Day 29 or visit or discontinued prematurely and have viral load data up to Day 8. For the analysis a cut-off date will be applied. All available data up to the cut-off date will be included in the analysis. The cut-off date is defined as the date when the last patient completed Day 29 visit or discontinued prematurely.
- The Part A final analysis will be performed when all patients completed the study at the final database lock (DBL). All data will be included in the analysis.
- Categorical data will be presented as frequencies and percentages for each category including a category labeled as “missing” when appropriate.
- Continuous variables will be presented with number of non-missing observations, mean, standard deviation, lower quartile (25th percentile), median, upper quartile (75th percentile), minimum, maximum.
- Unless otherwise specified, 95% confidence limits will be presented.

2.1.1 General definitions

2.1.1.1 Study treatment

Table 2.1-1 Investigational and control drug

Investigational/ Control Drug	Pharmaceutical Dosage Form	Route of Administration	Supply Type	Sponsor (global or local)
Ensovibep 15 mg/mL for Part A	Solution for infusion	i.v.	Non-blinded vials	Sponsor (global)
Placebo for Part A	Solution for infusion	i.v.	Saline infusion bag	Sponsor (global)
Ensovibep 15 mg/mL for Part B	Solution for infusion	i.v.	Double-blind vials	Sponsor (global)
Placebo for Part B	Solution for infusion	i.v.	Double-blind vials	Sponsor (global)

The investigational drug is ensovibep.

The formulation for Part A is 15 mg/mL ensovibep provided in isotonic buffer matrix [REDACTED]

The formulation for Part B is 15 mg/mL ensovibep provided in isotonic buffer matrix [REDACTED]

Isotonic saline will be used as placebo for Part A of the study. [REDACTED]

The terms study treatment and study drug are used throughout the document and refer to the infusion of double-blind treatment, i.e. Ensovibep/Placebo.

2.1.1.2 Treatment arms

Part A

Patients in Part A will be assigned on Day 1 at Visit 1 to one of the following four treatment arms in a ratio of 1:1:1:1 and will be dosed accordingly:

- Ensovibep 75 mg
- Ensovibep 225 mg
- Ensovibep 600 mg
- Placebo

Part B

Once the best safe and efficacious dose has been selected from Part A, patients in Part B will be assigned on Day 1 at Visit 1 to one of the following 2 treatment arms in a ratio of 1:1

- Ensovibep (best safe and efficacious dose, selected in Part A)
- Placebo

2.1.1.3 Study days

Study Day 1 (or Day 1 or reference start date) is defined as the day of first dose of study treatment.

All other study days are labeled as the number of days relative to Day 1. Therefore, for a particular date, study day will be calculated as follows:

- for dates on or after the date of first administration of study treatment:
Study day = Assessment date – date of study drug infusion + 1
- for dates prior to the date of first administration of study treatment:
Study day = Assessment date – date of study drug infusion

Moreover, duration of an event is calculated as:

Duration of an event = Event end date – event start date + 1.

2.1.1.4 Baseline

The baseline value is generally defined as the last non-missing value prior to the start of study drug infusion. If the date of assessment is the same as date of infusion but time is not available for comparison, the assessment is assumed to be prior to the administration of study treatment.

2.1.1.5 Post-baseline measurement

Post-baseline measurements are defined as assessments performed after start of study drug infusion.

When change from baseline is of interest the following formula will be used for each scheduled visit and time-point where baseline and post-baseline values are both available:

Change from baseline = post-baseline value – baseline value.

2.1.1.6 Visits

Measurements will be collected with the windowing defined in the protocol and outlined in Table 2.1-2.

Table 2.1-2 Visit windows

Visit label	Visit collection window (study days)
Screening	-3 to -1
Day 1	1
Day 3	3
Day 5	5
Day 8	8 ± 2
Day 15	15 ± 3
Day 22	22 ± 4
Day 29	29 ± 5
Day 61	61 ± 5

EOS (Day 91)	91 ± 7
--------------	--------

Visit labels as reported in the eCRF will be used for analysis. Discontinuation visits will be mapped to the next scheduled visit, if within modified protocol defined visit window, otherwise these will be handled as unscheduled visits. For the mapping the following modification will be applied to the protocol defined windows to avoid overlapping days: Day 22 (22 ± 3) and Day 29 ($29 -3/+ 5$) and Day 61 (± 7).

For ePRO data visits is not captured on the eCRF, visits will be assigned using ePRO assessment dates based on the modified protocol defined window.

Efficacy outputs will not include unscheduled visits. For laboratory and safety outputs, unscheduled visit information will be used in the summaries of the worst post-baseline measurement. Further details will be found in the respective Sections.

2.1.1.7 On-treatment/Treatment-emergent

If not stated otherwise, all post-baseline measurements will be considered as on-treatment/treatment emergent and included in the analyses.

A treatment-emergent adverse event (TEAE) is defined as any AE that started after the start of study drug infusion. If the AE start date is the same as date of infusion but time is not available for comparison, the AE will be considered to be treatment emergent.

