**Table 8-1 Part A: Assessment schedule**

Visit Name	S1 [6]	V1		V2	V3	V4	V5	V6	V7	V8	V9
Study Day	-3 to -1	1		3	5	8 ± 2	15 ± 3	22 ± 4	29 ± 5 (EOS) [7]	61 ± 5	EOS[8] / 91 ±7
		pre-dose	post-dose								
STUDY ENTRY AND GENERAL ASSESSMENTS											
Informed consent	(X)	X									
Inclusion/Exclusion criteria	(X)	X									
Demographics	(X)	X									
Complete medical history	(X)	X									
INVESTIGATIONAL PRODUCT											
Ensovibep (MP0420)/Placebo			X								
SAFETY ASSESSMENTS											
Prior/concomitant medication evaluation	Continuous starting after ICF signature, until 3 months after study medication										
Prior/concomitant hospitalization and procedures	Continuous starting after ICF signature, until 3 months after study medication										
AE evaluation	Continuous starting after ICF signature, until 3 months after study medication										
Local tolerability			X								
Physical examination and vital signs [1]	(X)	X									
General physical appearance and vital signs [1]				X	X	X	X		X		X
Body temperature, respiratory rate, oximetry	(X)	X		X	X	X	X		X		X

Visit Name	S1 [6]	V1		V2	V3	V4	V5	V6	V7	V8	V9
Study Day	-3 to -1	1		3	5	8 ± 2	15 ± 3	22 ± 4	29 ± 5 (EOS) [7]	61 ± 5	EOS[8] / 91 ±7
		pre-dose	post-dose								
Weight	(X)	X									X
Height	(X)	X									
Hematology, chemistry and coagulation safety tests		X		X			X		X	X	X
Pregnancy test in WOCBP [2]	(X)	X									X
Birth Control	Continuous until EOS [3]										
	VIROLOGY & SEROLOGY ASSESSMENTS										
Rapid SARS-CoV-2 antigen test	(X)	X									
SARS-CoV-2 sample (quantitative RT-PCR, mutation analysis)		X		X	X	X	X		X		X
PK blood sample		X	XX [4]	X		X	X		X	X	X
Blood sample for serum biomarkers		X		X		X	X		X		X
	CLINICAL ASSESSMENTS										
Symptom score [5]		X		Daily assessment				X	X		

Visit Name	S1 [6]	V1		V2	V3	V4	V5	V6	V7	V8	V9
Study Day	-3 to -1	1		3	5	8 ± 2	15 ± 3	22 ± 4	29 ± 5 (EOS) [7]	61 ± 5	EOS[8] / 91 ±7
		pre-dose	post-dose								

[REDACTED]; AE=adverse event; EOS=end-of-study; FDA=Food and Drug Administration; ICF=informed consent form; PCR=polymerase chain reaction; PK=pharmacokinetics; PRO=patient-reported outcome; RT=reverse transcriptase; S=screening; [REDACTED]; V=visit; WOCBP=women of child-bearing potential.

1. Vital signs consist of systolic and diastolic blood pressure and heart rate.

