2. Urine test with minimum sensitivity 25 mIU/mL for WOCBP in stable contraception for at least 3 months before screening and at EOS. Serum test in other cases, e.g., no previous contraception or unstable (e.g., due to missed days of oral contraceptive or change in contraceptive method).
3. Birth control method will be documented only in source data.
4. Two PK samples: 15 minutes and 90 minutes after end of administration (defined as end of the saline flush).
5. FDA's recommended 14-item symptom assessment ([FDA 2020a](#)) to be used (from which the 8-point score can also be extracted). Options: Daily documentation by patient until Day 15 via PRO-tool, then weekly; or dedicated phone assessment on pre-specified days.
6. Although it is anticipated that most patients will be screened and administered study medication on the same day (Day 1) at Visit 1, patients may have screening procedures performed up to 3 days before study medication administration (Days -3 to -1) and study medication administered on Day 1. The following screening procedures do NOT need to be repeated pre-dose in such case: Informed consent, demographics, complete medical history, height, and weight.
7. Patients who discontinue before Day 29 will complete all V7 (Day 29) assessments as their EOS visit except for the Long-COVID-19 or SF-36 questionnaires.
8. Patients discontinuing between Day 29 and Day 91 to complete V9 (Day 91) assessments as EOS visit.

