## 10 Safety monitoring and reporting

### 10.1 Definition of adverse events and reporting requirements

#### 10.1.1 Adverse events

An adverse event (AE) is any untoward medical occurrence (e.g., any unfavorable and unintended sign [including abnormal laboratory findings], symptom or disease) in a clinical investigation patient after providing written informed consent for participation in the study. Therefore, an AE may or may not be temporally or causally associated with the use of a medicinal (investigational) product.

The investigator has the responsibility for managing the safety of the individual patient and identifying and documenting AEs.

Qualified medical personnel will be readily available to advise on trial-related medical questions or problems.

Throughout the study, the investigator will determine whether any AEs have occurred by evaluating the participant. These events may be directly observed, reported spontaneously by the patient or by questioning the patient at each study visit or by laboratory test findings. Patients should be questioned in a general way, without asking about the occurrence of any specific symptoms.

Note that any symptoms collected by the PROs (see [Section 8.3.3](#)) will not be considered AEs and will not be reconciled with AEs.

Adverse events should be described using a diagnosis whenever possible, rather than individual underlying signs and symptoms. Adverse events must be accompanied by the following information (as far as possible):

1. Intensity, graded according to the Common Terminology Criteria for Adverse Events (CTCAE) version 5.0
2. Its causal relationship to the study treatment. If the event is due to lack of efficacy or progression of underlying illness (i.e., progression of the study indication) the assessment of causality will usually be 'Not suspected.' However, worsening of COVID-19 that exceeds anticipated fluctuations or course of the disease should be documented as AE, and may qualify as an adverse event of special interest (AESI) (see [Section 10.1.4](#)).
3. Its duration (start and end dates) or if the event is ongoing, an outcome of not recovered/not resolved must be reported
4. Whether it constitutes a SAE (see [Section 10.1.2](#) for definition of SAE, and [Section 10.1.3](#) for SAE reporting) and which seriousness criteria have been met
5. All AEs must be treated appropriately. Treatment may include interrupting or withdrawing of study drug
6. Its outcome

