Relevant conditions apart from COVID-19 infection, which were already present at the time of informed consent should be recorded in medical history of the patient. However, worsening of these conditions after study start should be recorded as an AE.

Adverse event monitoring should be continued until EOS visit (see [Table 8-1](#)). After the EOS, only serious events assessed as related to study drug should continue to be reported, and only to the safety database.

Once an AE is detected, it must be followed until its resolution or until it is judged to be permanent (e.g., continuing at the end of the study), and assessment must be made at each visit (or more frequently, if necessary) of any changes in severity, the suspected relationship to the interventions required to treat it, and the outcome.

Information about adverse drug reactions for the investigational drug can be found in the IB.

Abnormal laboratory values or test results constitute AEs only if they fulfill at least one of the following criteria:

- they induce clinical signs or symptoms
- they are considered clinically significant
- they require therapy

Clinically significant abnormal laboratory values or test results must be identified through a review of values outside of normal ranges/clinically notable ranges, significant changes from baseline or the previous visit, or values which are considered to be non-typical in patients with the underlying disease.

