2.8.3 Laboratory data

Laboratory data include measurements of all parameters below:

Test Category	Test Name
Hematology	Hematocrit, Hemoglobin, Platelets, Red blood cells, White blood cells, Differential (Basophils, Eosinophils, Lymphocytes, Monocytes, Neutrophils, Other)
Chemistry	Albumin, Alkaline phosphatase, ALT, AST, Gamma-glutamyl-transferase (GGT), Lactate dehydrogenase (LDH), Bicarbonate, Calcium, Magnesium, Phosphorus, Chloride, Sodium, Potassium, Creatinine, Creatine kinase, Direct Bilirubin, Total Bilirubin, Total Protein, Blood Urea Nitrogen (BUN) or Urea, Uric Acid, Amylase, Lipase, Glucose (non-fasting), CRP, D-Dimer, Ferritin
Coagulation	Prothrombin time (PT), International normalized ratio [INR], Activated partial thromboplastin time (APTT)
Pregnancy Test	Serum / Urine pregnancy test

Clinically notable abnormalities and abnormalities in liver function tests (LFT) are described in [Section 5.5](#).

Absolute values and change from baseline will be summarized for continuous laboratory parameters by treatment and scheduled visit, including the worst post-baseline value. The direction of interest for worst post-baseline value for selected hematology and biochemistry parameters is shown in [Section 5.4](#).

For selected laboratory tests, the number and percentage of patients with newly occurring or worsening laboratory abnormalities meeting the clinically notable criteria at any time post-

baseline, considering all post-baseline data from scheduled, unscheduled and premature discontinuation visits, will be summarized by treatment and laboratory parameter.

Furthermore, the number and percentage of patients with newly occurring or worsening abnormalities in liver function tests (LFT) will be summarized by treatment and at any time post-baseline considering all post-baseline data from scheduled, unscheduled and premature discontinuation visit.

The number (%) of patients with newly occurring or worsening of notable laboratory values will be provided.

Shift tables using the low/normal/high/ (low and high) classification will be used to compare baseline to the worst post-baseline value.

Listing of all laboratory data of patients with notable abnormal laboratory values will be provided with the classifications relative to the laboratory normal ranges.

Urine pregnancy test data will be summarized using frequency and percentage by treatment. A listing of all pregnancy test data will be provided.

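### The SAP classes an AE as treatment-emergent by start date alone, so an AE that begins between consent and infusion and worsens afterwards on the same record is left out of the treatment-emergent tables

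*SAP*

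**What the plan says.** The operative definition is in SAP 2.1.1.7: "A treatment-emergent adverse event (TEAE) is defined as any AE that started after the start of study drug infusion". The same section adds that if an AE starts on the day of infusion and "time is not available for comparison, the AE will be considered to be treatment emergent". Protocol 12.5.2 uses the term treatment-emergent without defining it.

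AE collection begins earlier. Protocol 10.1.1 defines an AE as an occurrence "in a clinical investigation patient after providing written informed consent for participation in the study", and Protocol Table 8-1 gives the AE collection period for Part A as "Continuous starting after ICF signature, until 3 months after study medication". A footnote to that table says that "patients may have screening procedures performed up to 3 days before study medication administration", although most patients are expected to be screened and dosed on Day 1.

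For an AE once detected, Protocol 10.1.1 says that "assessment must be made at each visit (or more frequently, if necessary) of any changes in severity". Its separate instruction to record worsening as an AE applies to relevant conditions other than COVID-19 that were "already present at the time of informed consent should be recorded in medical history of the patient".

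SAP 2.8.1 heads its main summaries of TEAEs, SAEs and AESIs as treatment-emergent. It lists all AEs, SAEs and AESIs, with treatment-emergent ones flagged. For laboratory data, SAP 2.8.3 counts "newly occurring or worsening laboratory abnormalities meeting the clinically notable criteria"; SAP 2.8.4.1 takes the same approach to vital signs.

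**The concern.** There is an interval between consent and infusion in which AEs are recorded but cannot be treatment-emergent, whatever happens to them later. If such an event is aggravated after dosing, the part that could be a drug effect occurs on treatment, yet the event is classified by a date before treatment. Randomization should balance the pre-infusion events themselves across arms. Aggravation caused by the drug would arise only in the ensovibep arms, so leaving it out can only undercount it.

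What is at stake is the completeness of the main safety tables. The primary efficacy analysis and patient management are not affected.

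**Working it through.** No formula applies and the plan gives no figure to reproduce. The check is to follow different kinds of event through the recording rules and then through the SAP definition.

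| Event | How it is recorded or dated | Treatment-emergent under SAP 2.1.1.7? |
|---|---|---|
| Non-COVID-19 condition present at consent, worsens after dosing | Worsening entered as an AE (Protocol 10.1.1), so onset is after infusion | Yes |
| COVID-19 worsening after dosing beyond the anticipated course | Documented as an AE (Protocol 10.1.1); an AESI if moderate or severe with onset within 1 week of study drug (Protocol 10.1.4) | Yes |
| AE starting on Day 1, start time not available | Assumed to follow the start of infusion (SAP 2.1.1.7) | Yes |
| AE with partial start date in the infusion year, month missing or equal to the infusion month | Imputed to the day after treatment start (SAP 5.1.2) | Yes |
| AE with known start between consent and infusion, worsens after infusion, site opens a new record | New record carries a post-infusion start | Yes |
| The same AE, worsening kept on the original record | Pre-infusion start is retained | No |

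Only the last row falls through. Three points show that it can occur under the documents as written.

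1. The interval exists. It is 0 to 3 days by the Table 8-1 footnote. For a patient consented and dosed on Day 1 it is the time between the two, and an AE with a recorded time in that gap counts as pre-infusion.

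2. The protocol's worsening rule does not reach it, because that rule is tied to conditions present at consent. An AE that begins after consent is followed for changes in severity, with no instruction to open a new record or reset the start date. For SAEs, Protocol 10.1.3 directs progression of an initial SAE to the original episode.

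3. Nothing later in the SAP brings it back into the main tables. SAP 2.8.1 applies the treatment-emergent restriction to the TEAE, SAE and AESI summaries, and SAP 5.1.2 changes only partial dates.

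The restriction is not universal. The SAP's sentence on summarizing deaths, and the AESI and safety-topic summaries in SAP 2.8.1.1, do not restate it, so an affected event could still appear there.

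**The case against.** The strongest reply is that the last row of the table depends on eCRF record-keeping that the documents do not show. A visit-by-visit severity assessment does not establish that one record is kept. Protocol 10.1.2 includes worsening of something pre-existing in the SAE definition, and Protocol 10.1.3 also asks for an SAE in a different time interval to be reported as a new event. A site that opens a new record at worsening would produce a TEAE under the present wording. This stands as a condition on the point. It does not remove it, because no passage requires a new record for this case.

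A second reply is that the SAP already leans toward inclusion for untimed and partly dated events, and that all AEs are listed. This is correct and narrows the group to AEs with a known pre-infusion start.

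A third is that laboratory values are repeated measurements with a baseline, while AEs are event records, so different rules are not a contradiction. That is fair. The laboratory rule shows that the SAP counts worsening elsewhere; it does not make the AE rule an internal error.

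A reader might also infer that many events are missed because patients are enrolled early in an acute illness, when new symptoms are frequent. The documents do not support this. Protocol 10.1.1 says symptoms collected by the patient-reported questionnaires are not AEs, and COVID-19 worsening beyond its anticipated course is documented as an AE with its own post-dose onset. What remains is mainly non-COVID-19 AEs.

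**Conclusion.** The point holds as a narrow gap in a definition. Applied as written, SAP 2.1.1.7 leaves out of the treatment-emergent tables an AE with a known start between consent and infusion that increases in grade or becomes serious afterwards on the same record. This assumes that the eCRF keeps one record in that situation.

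Its size cannot be estimated from the documents, which give neither the proportion screened early, nor the frequency of pre-infusion AEs, nor the proportion that worsen. Purely as illustration, take 10% to 50% screened early, 2% to 10% of those with a pre-infusion AE, and 10% to 30% of those worsening:

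- Part A: 400 × 0.10 × 0.02 × 0.10 = 0.08 to 400 × 0.50 × 0.10 × 0.30 = 6 patients.
- Part B: 1717 × 0.10 × 0.02 × 0.10 = 0.3 to 1717 × 0.50 × 0.10 × 0.30 = 26 patients.

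All three rates are assumptions, the range includes practically none, and 50% screened early fits poorly with the protocol's expectation of same-day dosing for most patients. A reader might conclude that the safety tables are materially biased toward no effect. Nothing in the documents supports more than the direction: if there is an effect, drug-related aggravation is undercounted. This is a worthwhile clarification of low severity.

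**What to change.** In SAP 2.1.1.7, define a TEAE as an AE that starts after the start of infusion, or one that starts before it and increases in CTCAE grade or becomes serious after it.

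For Part A, apply the definition where dated changes in grade or seriousness are in the database; elsewhere, identify such events in the listings. A site instruction can do little here, since 381 patients had been treated by 19-Oct-2021 according to the protocol's amendment rationale.

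For Part B, put the definition in the SAP amendment that SAP Section 1 already promises before the first patient's first visit. Add an eCRF completion note that worsening after infusion of an AE that began before it is entered as a new AE record.

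The cost is a small amount of derivation work and a short site instruction. For Part A the reach of the derivation depends on whether dated changes were captured, which should be confirmed first.
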